9.6 Blinding

Study condition will not be blinded in this trial.

9.7 Participant Compensation

All participants will receive the following compensation for time and effort related to research activities (although various sites may offer slightly different amounts depending on the appropriateness of compensation rates in their setting); \$50 for assessments at baseline. treatment weeks 4, 8, 12, and 3- and 6-month post treatment follow-up visits (participants will receive an additional \$50 bonus if they complete all of these assessment visits). The maximum compensation for assessments is \$350. In addition, all participants will be compensated \$5 for each urine sample they provide during the 12-week treatment phase (a maximum of 24 urine screens for a total of \$120). To avoid competing with the potential treatment effect of the contingency management component in the modified TAU + TES condition, compensation for providing urine samples will be given to all participants at the monthly treatment phase visits (i.e., weeks 4, 8, and 12). Each CTP can determine whether participant compensation for assessment is made in cash or voucher depending on what is most appropriate for their site. As is typical in many clinical trials, providing compensation to all study participants will help ensure we obtain study data critical for evaluation of our planned interventions. We expect that this aspect of the intervention should not greatly impact the planned economic analyses, as both groups of participants will receive compensation for assessments and we do not expect this to differ across groups. Also, these assessments and the associated compensation for completing them would not be needed in routine clinical practice and thus would not be associated with the cost of implementing such interventions in real-world settings.

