7.2 Planned Assessment for Effectiveness Analyses

7.2.1 Substance Use Outcomes based on Urine Toxicology, Breath Alcohol, & Self-Report (10 min)

Urinalysis and breathalyzer will occur at the baseline visit, twice per week for 12 weeks of the active study phase, and at the 3-month and 6-month follow up visits (procedures will coincide with the timing of planned contingency management procedures designed to reinforce drug abstinence). Each urine sample will be tested for the presence of 10 drugs: cocaine, opiates 2000 ng (includes morphine, codeine, and heroin), amphetamines, cannabinoids (THC), methamphetamines, benzodiazepines, oxycodone, methadone, barbiturates, and MDMA. A

breathalyzer will be used to screen for blood alcohol concentration (BAC), scored as negative versus positive for blood alcohol according to the standard cutoff. Participants whose BAC is above a .08 (standard legal limit) will be asked to wait to complete any additional assessments until their BAC is below .08 to ensure that participants are not intoxicated during the completion of the assessment measures. The intoxication event should be recorded in the progress notes. Research staff will use clinical judgment as whether participants can reasonably complete assessments with BAC levels above .01 but below .08.

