Participants in Condition 2 will earn incentives contingent upon objective evidence of abstinence from their primary substance of abuse in accordance with an intermittent schedule of reinforcement shown to be efficacious in a prior CTN study conducted at CTPs ("fishbowl" prize system; Petry et al., 2005a). Specifically, participants will receive prize incentives for providing urine samples negative for their primary substance of abuse (as assessed on the DSM-IV Checklist), or breath samples negative for alcohol if alcohol is their primary substance of abuse (samples collected twice per week). As various participants in community-based outpatient substance abuse treatment will likely be in treatment for different substances of abuse, these procedures will be used to ensure that contingencies target the various substances of choice among this heterogeneous sample and that results will be generalizable to diverse sub-groups of substance-using individuals. If urine specimen results are ambiguous, inconclusive, or invalid (as described in Section 7.2.1), participants will be offered the opportunity to provide a second sample. If they choose not to do this, their sample will be counted as missing for that day (and positive for purposes of incentive procedures).

Contingency management interventions have been shown to be efficacious in targeting this array of substances in prior research (see Stitzer & Petry, 2006 for a review). In this process, each time a participant provides a urine/breath sample that is negative for their primary substance of choice, s/he will receive a draw from the computerized 'prize bowl' included in TES, which allows for automation of all prize calculation & tracking on any desired probability

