14.14.4 Power for Economic Hypothesis

We estimate the power for the outcome of cost for increased rate of abstinence at Week 12 given the target sample size of about 500 (about 250 participants per group). The primary effectiveness measure will be abstinent weeks. As above, we assume 2.4 weeks for TAU (SD=3.38) and 3.6 weeks for TAU+TES (SD=3.87). We use a standard deviation of 3.63. The additional costs over 12 weeks are assumed to be \$467 (SD=374) in the TAU group and \$823 (SD=659) in the intervention group. These numbers are derived from the TAU costs of the 12 week CM interventions for (1) cocaine abuse (2) and stimulant abuse. The expected CM payout is \$293 with 55% compliance assumed. The TAU+TES group also includes higher TAU treatment costs due to greater retention of 42% and a 20% reduction in TAU treatment costs from "reduced" TAU. The final parameter for estimating power in cost-effectiveness is the correlation between costs and effects. Because CM costs are highly likely to cost more for the most successful clients (greater payouts and greater treatment duration) there is a strong positive correlation. We assume a correlation coefficient of 0.15.

Using the equation for power for cost-effectiveness ratios (Glick et al., 2001), we find 96% power with a proposed sample size of 500. The study is powered at 90% for a cost effectiveness ratio of costs per abstinence week of \$920 per abstinence week.

Note on power for cost-effectiveness. A cost-effectiveness ratio is powered relative to its maximum acceptable value. The range of maximum acceptable values typically used is \$50,000 to \$100,000 per quality adjusted life year (QALY). However, clinical trials in the substance abuse research field generally have not used QALYs or even life years saved as a measure of effectiveness (as is often done in other areas of medicine). This is true for this project as well where the primary clinical outcome is a continuous drug free week. Recent data from a CTN study using QALYs found that for every 15 percentage point increase in the rate of abstinence (which converts to 1.8 weeks over 12 weeks), QALYs increased by 5 percentage points. We translate the \$50,000 per QALY threshold to \$1,400 per week of abstinence.

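### The drug screens that trigger the TAU+TES prize draws drop out of, or largely cancel from, the incremental cost, so that cost is understated by the testing beyond each site's routine

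*Protocol*

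**What the plan says.** Section 9.7 describes "compensation for time and effort related to research activities". It lists $50 per assessment visit and then, separately, $5 per urine sample ("a maximum of 24 urine screens for a total of" $120). It gives two reasons why this should hardly affect the economic analysis. The first is that "both groups of participants will receive compensation for assessments and we do not expect this to differ across groups". The second is that "these assessments and the associated compensation for completing them would not be needed in routine clinical practice", so that no implementation cost attaches to them.

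Section 7.2.1 places the screens among the planned assessments: "Urinalysis and breathalyzer will occur at the baseline visit, twice per week for 12 weeks of the active study phase". The same sentence adds that the "procedures will coincide with the timing of planned contingency management procedures designed to reinforce drug abstinence". The assessment schedule lists the urine and alcohol screens too, and Section 5.2 asks for them in both arms.

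In TAU+TES only, Section 9.4.1.2(c) states that "participants will receive prize incentives for providing urine samples negative for their primary substance of abuse", or negative breath samples where alcohol is the primary substance. Two bonus draws follow when samples are negative for all tested substances. TAU receives no incentives (Section 9.4.1.1).

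Section 14.14 says that the cost-effectiveness ratios are meant to inform adoption. Section 14.14.1 costs resource units counted from site forms for study-delivered services. It does not say how screens are to be charged to the arms.

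**The concern.** A program that adopts TES with its abstinence incentives has to run the screens, because without a result no abstinence draw can be awarded. The bonus draws need the full panel, not only the test for the primary drug. Screening is therefore an input to one arm's intervention as well as a research measurement in both arms. The trial's design hides the first role behind the second, because the control arm is screened on the same schedule for outcome purposes.

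At stake is the numerator of the ratio. The 8 ratios in Section 14.14.3 all contain the cost of the 12-week treatment phase, so they share the problem. It matters most for the treatment program's perspective, since the program would be the one paying for the tests.

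**Working it through.** **1. The two possible treatments of screening cost.** Let u be the cost of one screen (supplies and staff time), n1 and n0 the screens taken in TAU+TES and TAU, and r the screens a TAU patient would have had under the site's routine practice.

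- What an adopting program would face: u × (n1 − r).
- If Section 9.7 removes the screens: the contribution is 0, and the shortfall is u × (n1 − r).
- If Section 14.14.1 counts them as study-delivered services in both arms: the contribution is u × (n1 − n0), and the shortfall is u × (n0 − r).

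With identical schedules, n1 and n0 differ only through attendance, so the second route largely cancels. Under either route the cost is understated as long as routine testing is less frequent than the trial's. The shortfall is nil if sites already test that often.

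**2. The plan's own figure.** The inputs are in Section 14.14.4: TAU cost $467, TAU+TES cost $823, prize payout $293, and abstinent weeks 2.4 and 3.6. The section describes the build: "The TAU+TES group also includes higher TAU treatment costs due to greater retention of 42% and a 20% reduction in TAU treatment costs".

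- 467 × 1.42 × 0.80 = 530.51
- 530.51 + 293 = 823.51, which reproduces the stated $823
- Cost difference: 823 − 467 = $356
- Effect difference: 3.6 − 2.4 = 1.2 weeks
- Planning ratio: 356 / 1.2 = $297 per abstinent week

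The terms described account for the whole $823, so no term is added for screening.

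**3. Illustration of size.** The protocol gives no unit cost; $5 to $20 per screen is an assumption. The upper count of 24 is the schedule. The lower count of 12 applies the 50% missing rate that Section 14.4.1 uses for power. Routine testing is set to r = 0, the setting that gives the largest shortfall.

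| Unit cost | Screens | Added cost | Cost difference | Per abstinent week |
|---|---|---|---|---|
| none | none | $0 | $356 | $297 |
| $5 | 12 | $60 | $416 | $347 |
| $5 | 24 | $120 | $476 | $397 |
| $10 | 24 | $240 | $596 | $497 |
| $20 | 24 | $480 | $836 | $697 |

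**4. Distance to the protocol's reference values**, at 24 screens and r = 0:

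- $920 per week is reached at (920 × 1.2 − 356) / 24 = $31 per screen.
- $1,400 per week is reached at (1,400 × 1.2 − 356) / 24 = $55 per screen.

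**5. Whether the data to correct this are collected.** Screens are recorded on their own forms, so n1 and n0 will be known. The contents given for the DATCAP (Section 7.3.3) and the TAU tracking form (Sections 7.2.8 and 9.4.1.1) do not name drug testing, so r is not visibly captured.

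**The case against.** The strongest reply is textual. Within Section 9.7 the word assessments may mean only the $50 visits. The stated maximum of $350 for assessments equals 6 × 50 + 50 and leaves out the urine money, which is introduced as an addition. Sections 5.2 and 9.4.1.2 also speak of giving samples and completing assessments as two things. A reader might infer that the plan definitely classes the screens as research-only; the text does not settle that. The point survives this reply. Sections 7.2.1 and 9.2 and the schedule do class screens as assessments. Under the narrower reading, following Section 14.14.1 literally counts the screens in both arms and largely cancels them.

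A second reply is that itemised price weights belong in a statistical analysis plan. That holds for the list of prices. It does not cover a stated reason for exclusion that conflicts with how the intervention works.

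A third is that $823 is a power input, not the definition of the costs to be analysed. That stands. The figure also has no term for the TES platform, yet Sections 7.3.3 and 14.14.5 plan to measure or vary TES costs. Whether the $467 already includes some testing cannot be seen. A reader might take the $823 as proof that the analysis omits screening; it only corroborates the point.

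A fourth is that TAU programs may already test. That also stands. Section 6.5 excludes sites that routinely offer contingency management, not sites that routinely test, so one cannot infer that a TAU program needs no screens. Only the excess over routine testing is at issue.

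**Conclusion.** The point holds in direction. Screens are required to award abstinence incentives in TAU+TES, and neither route in the protocol charges them to that arm as an intervention cost. The incremental cost is understated by the testing that exceeds each site's routine.

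The size is not established. The range of $347 to $697 per abstinent week, against $297 on the planning inputs, rests on an assumed unit price, an assumed count and no routine testing. A reader might infer that TES would stop looking cost-effective once screening is charged. The documents do not support that: even the top of the range is about half of $1,400, and roughly $55 per screen would be needed to reach it. The $5 payments to participants are properly research-only and are no part of the shortfall.

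This concerns a secondary economic analysis. It is worth correcting because that analysis is meant to guide adoption and the correction is cheap.

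**What to change.** - In Section 9.7, limit the exclusion to the $50 assessment visits and the $5 sample payments.
- In Section 14.14.1, state that screens needed to deliver incentives in TAU+TES (supplies and staff time) are intervention costs in both perspectives, that TAU is charged only for the site's routine testing, and that research-only TAU screens are excluded.
- Add one site-level item on routine testing frequency, for example on the DATCAP.
- Report the ratio with and without screening cost.

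Nothing need be added for counselor check-ins, since their minutes (Section 10.0) and counselor hours (Section 7.3.3) are already recorded.

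The cost is one added item, a few price weights and some wording. Screen counts are already collected and no study procedure changes. The ratio will look less favourable wherever testing exceeds routine.

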10.0 TREATMENT FIDELITY & ADHERENCE

As previously discussed, by automating the CRA + incentives psychosocial intervention with TES, the fidelity of the delivery of the intervention is assured. Indeed, the computerized delivery of CRA helps reduce concerns about fidelity in the delivery of the intervention and all incentives earnings will be calculated via pre-established earnings probabilities for the various target behaviors (as described in Section 9.4.1.2). To monitor participant adherence, the electronic progress reporting system within TES will enable automated tracking of participant activity using TES. This tracking system will enable research staff to view information regarding what modules participants have accessed and/or completed and how long they spent in computer sessions. As previously noted, data from this tracking system will be used to assess participant's "dose" of exposure to TES in planned analyses.

TAU will not be manualized to better reflect how TAU is provided within CTPs and thereby increase the generalizability of study results. Note that, in addition to the automated tracking of participant activity with the web-based intervention, our research staff will obtain attendance records of participants in group and/or individual counseling sessions from each CTP, along with information on the duration of each session. The research team will document this information about provider contact with patients in both the TAU and the modified TAU + TES condition (using the TAU Tracking form created for this purpose and described in the assessment section). All CTP counselors will be asked to "check-in" with clients who are randomized to the TES+TAU arm and complete a brief counselor checklist (including approximate number of minutes spent discussing TES). The check-in will include an inquiry about the TES experience, updates on module completion, and discussion of optional module completion, as appropriate. Counselors will receive reports from the research staff documenting which TES modules their individual clients have completed. This is intended to be consistent with the model of TES as "clinician extender" which is being tested in this trial.

Further, a clinical supervisor at each site will receive training from the Lead Node in overseeing counselor interactions with TES clients. Supervisors will be trained in reviewing completion of the counselor checklist and discussing with counselors how the information from TES reports is being used in the counseling sessions. Clinical supervisors will meet with counselors monthly to discuss and monitor interactions with TES clients.

11.0 TRAINING PROCEDURES

All research staff will be thoroughly trained on all study procedures, including Informed Consent, the use of TES, and participant tracking procedures. Additionally, counselors at each collaborating CTP will be thoroughly trained in the study design, human subject's protection, their role in each of the two study conditions, and how to review their clients' activity reports within TES. Research staff will also be trained on all assessment measures, including assessments administered via computer, to be able to answer all participant questions.

12.0 CONCOMITANT THERAPY

12.1 General Considerations

To avoid placing artificial constraints on the study design and reduce the generalizability of study findings, we will not exclude participants who engage in substance abuse treatment or psychiatric treatment outside of the study during the 12-week study phase. Rather, we will track the type, frequency, and duration of such concomitant therapy and consider these data in planned analyses as appropriate (via the NMS).

12.2 Medications Allowed During the Trial

We do not expect that many patients in CTPs will be receiving pharmacotherapy for substance use disorders (especially because individuals with opioid use disorders receiving opioid pharmacotherapy will not be eligible to participate in this trial). However, as previously noted, we will track this information for all participants and consider pharmacotherapy data in planned analyses as appropriate (via the NMS).

13.0 REPORTING AND MONITORING

13.1 Statement of Compliance

This trial will be conducted in compliance with the appropriate protocol, current Good Clinical Practice (GCP), the principles of the Declaration of Helsinki, and all other applicable regulatory requirements. Participating sites must obtain written approval of the study protocol, consent form, other supporting documents, and any advertising for participant recruitment from their local institutional review board (IRB) in order to participate in the study. Prior to study initiation, the protocol and the informed consent documents will be reviewed and approved by an appropriate Ethics Review Committee (ERC) or IRB. Any amendments to the protocol or consent materials must be approved before they are implemented. Annual progress reports and local Serious Adverse Event (SAE) reports will be submitted to each IRB, according to its usual procedures.

13.2 Regulatory Files

The regulatory files should contain all required regulatory documents, study-specific documents, and all important communications. Regulatory files will be checked at each participating site for the regulatory documents compliance prior to study initiation, throughout the study, as well as at the study closure.

13.3 Informed Consent

The informed consent form is a means of providing information regarding the trial to a prospective participant and allows for an informed decision about participation in the study. Each study site must have the study informed consent approved by their IRB(s). A copy of the IRB-approved consent, along with the IRB study approval, must be sent to the Clinical Coordinating Center (CCC) and the lead node (LN) prior to the site initiation visit. Every study participant is required to sign a valid, IRB-approved current version of the study informed consent form prior to the initiation of any study related procedures. The site must maintain the original signed informed consent for every participant in a locked, secure location that is in compliance with their IRB and institutional policies and that is accessible to the study monitors. Every study participant should be given a copy of the signed consent form.

Prior to signing the informed consent form, research staff that are knowledgeable about the study will explain the study to the potential participant and provide the participant with a copy of the consent to read. If the participant is interested in participating in the study, a researcher who is authorized to obtain informed consent by the PI and if applicable by the IRB, will review each section of the informed consent form in detail, answer any of the participant's questions, and determine if the participant comprehends the information provided by administering the comprehension tool. The participant will consent by signing and dating the consent document. The person obtaining consent and a witness, if required by the local IRB(s), will also sign and date the consent document. The consent must be properly executed and complete to be valid. It is strongly recommended that another research staff member review the consent after it is signed to ensure that the consent must be listed on the Staff Signature Log and must be approved by the IRB, if required. All persons obtaining consent must have completed appropriate training.

In order to ensure that potential study participants understand the research study, a comprehension "quiz" (referred to as a comprehension tool) will be administered to potential participants prior to the informed consent being signed. If the potential participant misses an item on the quiz, the research staff will re-review that information to ensure understanding of

study procedures and have the person re-take the consent quiz prior to signing the informed consent document. The content of the quiz may be modified per local IRB requirements.

The informed consent form must be updated or revised whenever important new safety information is available, or whenever the protocol is amended in a way that may affect a participants' participation in the trial. A copy of the informed consent will be given to a prospective participant to review during the consent process and to keep for reference. The participant will be informed that their participation is voluntary and they may withdraw from the study at any time, for any reason without penalty.

Individuals who refuse to participate or who withdraw from the study will be treated without prejudice. Study sites will be responsible for maintaining signed consent forms as source documents for quality assurance review and regulatory compliance.

